13.3 Relationships between parameters and covariates

Relationships between PK parameters and covariates such as dose level, weight, age, indication, as well as relationships between emerging observations of safety (e.g. IRR, cytokines, QTcF), efficacy or pharmacodynamic biomarkers (e.g. peripheral blood B-cells and CH50) and plasma exposure will be explored graphically by the sponsor. If deemed relevant, these relationships may be further investigated by population modelling approaches.

14 Interim Analyses

DLTs will be evaluated after the completion of DLT observation periods for each dose level cohort, using the mBOIN approach, during the Dose Escalation part.

A single interim analysis will be performed during the Dose Expansion part, to analyse the safety data after 20 subjects have completed 2 cycles.

No other formal interim analyses are planned for this trial.

14.1 DLT Evaluation during Dose Escalation part

After all subjects within a dose cohort have completed the DLT observation period as described in Section 5.8, the Dose Escalation Committee (DEC) will review the data and propose initiation of the

next dose cohort (as appropriate). The sponsor's Safety Committee must endorse the proposal before the next dose cohort can begin enrolling.

Dose escalation will be conducted following an mBOIN design, as described in protocol 4.1.1.1 and Yuan et al 2016 [5]. After the DLT observation period has been completed for a given cohort, the frequency of DLTs in that dose level will be evaluated to determine if the next cohort should stay on the same dose, escalate to the next higher dose level, or de-escalate to the next lower dose level.

Based on a target toxicity level of 25%, the mBOIN design results in an escalation border of $\lambda_1 = 0.197$ and $\lambda_2 = 0.298$, as stated in the protocol. To summarize, if the DLT frequency is ≤ 0.197 , escalation would be recommended; $0.198 - 0.297$ would indicate staying at the same dose level; and DLT frequency ≥ 0.298 would suggest a de-escalation.

Further, a certain dose level can no longer be investigated if an additional DLT-free cohort on the same level would lead to de-escalation. This is summarized in Table 10 of the protocol. For example, a cohort of 3 people experiencing 3 DLTs might be de-escalated, and the next lower cohort meet criteria for escalation; if 3 more people were added to the higher cohort, the 3 DLTs among now 6 subjects would automatically meet de-escalation criteria. Therefore, once 3 DLTs are experienced in a cohort of 3, that dose level is terminated.

Following the completion of the DLT observation period, the Dose Escalation Committee will recommend the dose level for the next cohort of subjects, based on the mBOIN algorithm recommendation and a review of the safety data. The DEC's recommendation will need to be endorsed by the Safety Committee before enrolling the next cohort.

The Dose-Determining Set is used for all analyses to support dose escalation decisions.

The following statistical summaries and listings may be presented. Dose escalation decisions may also be made based on raw data listings from the clinical database.

- Summary of subject demographics
- Summary of TEAEs during the DLT observation period
- Listing of adverse events, by dose level cohort and subject

14.2 *Interim Analysis during Dose Expansion part*

The objective of the interim analysis during the Dose Expansion part is to evaluate safety data.

This analysis will be performed after 20 subjects (across the 3 diagnosis cohorts) have been exposed and followed for 2 cycles. Subjects who have been treated, but withdrawn from the study prior to the end of the second cycle, will be included.

The cut-off date for the interim analysis will be based on the 20th subject in the Dose Expansion part completing the second cycle (i.e., 8 weeks after the first dose), with additional time allowed for data entry and cleaning as necessary.

This interim analysis is performed to review safety data. No pre-specified stopping criteria will be utilized.

The interim analysis results will be presented using the FAS or Safety Set, unless otherwise specified. The following statistical summaries and listings will be presented:

- Summary of subject accounting and disposition, using the FAS, as described in Section 6
- Summary of subject demographics, using the FAS, as described in Section 7

- Summary of TEAEs by SOC and PT, using the Safety Analysis set, as described in Section 11.1
- Listing of adverse events, by subject and time point

15 Statistical Analyses for Safety Monitoring

The statistical analysis for safety monitoring is specified in a separate DMC charter.

16 Data Exchange Procedures

All analyses will be communicated to the sponsor and DMC through the use of Clinipace's Secure File Exchange (SFE) site.

17 Software

The data will be analysed using SAS version 9.3 or higher.

18 Abbreviations

AE	Adverse Event
ADA	Anti-Drug Antibodies
AESI	Adverse Event of Special Interest
ATC	Anatomical Therapeutic Class
AUC _{0-7 days}	Area under the plasma concentration time curve, from 0 to 7 days (Cycle 1 Day 1 only)
AUC _{0-∞} (AUC _{inf})	Area under the plasma concentration time curve, from time 0 extrapolated to infinity
AUC _{0-last}	Area under the plasma concentration time curve, from time 0 to the last measurable non-zero concentration
CI	Confidence Interval
C _{max}	Maximum observed concentration of GEN3009
CMV	Cytomegalovirus
CR	Complete Response or Complete Remission
CRF	Case Report Form
CRO	Contract Research Organization
CTCAE	Common Terminology Criteria for Adverse Events
DDS	Dose-Determining Analysis Set
DLBCL	Diffuse Large B-cell Lymphoma
DLT	Dose Limiting Toxicity
DMC	Data Monitoring Committee
DOR	Duration of Response
ECG	Electrocardiogram
ECOG	Eastern Cooperative Oncology Group
EFF	Response-Evaluable set
FAS	Full analysis set
FDA	US Food & Drug Administration
FL	Follicular Lymphoma

HGBCL	High Grade B-cell Lymphoma
ICH	International Conference on Harmonization
IRC	Independent Review Committee
LLOQ	Lower Limit of Quantification
MedDRA	Medical Dictionary for Regulatory Activities
MRD	Minimal Residual Disease
MTD	Maximum Tolerated Dose
MZL	Marginal Zone Lymphoma
nPR	nodal Partial Remission
NE	Not Estimable
ORR	Overall Response Rate
OS	Overall Survival
PAS	Pharmacokinetic Analysis Set
PD	Progressive Disease
PK	Pharmacokinetics
PMBCL	Primary mediastinal B-cell Lymphoma
PR	Partial Response or Partial Remission
PT	Preferred Term
QTcF	Fridericia's correction to the QT interval
R/R	Relapsed or Refractory
RP2D	Recommend Phase 2 Dose
SAE	Serious Adverse Event
SAF	Safety analysis set
SAP	Statistical Analysis Plan
SD	Stable Disease
SFE	Secure File Exchange
SLL	Small Lymphocytic Lymphoma
SOC	System Organ Class
$t_{1/2}$	Terminal phase half-life
TEAE	Treatment Emergent Adverse Event
TLF	Tables, Listings, and Figures
T_{max}	Time of maximum observed concentration
TTNT	Time to Next Anti-Lymphoma Therapy
TTR	Time To Response
WHODRUG	World Health Organization Drug Dictionary

19 References

1. Standard Country or Area Codes for Statistical Use provided by the Statistics Division of the United Nations Secretariat (<http://unstats.un.org/unsd/methods/m49/m49regin.htm>)
4. U.S. Food and Drug Administration. *Clinical Trial Endpoints for the Approval of Non-Small Cell Lung Cancer Drugs and Biologics Guidance for Industry*. Apr 2015. <https://www.fda.gov/media/116860/download>

20 Appendices

Appendix I: Progression and Censoring Criteria for Analyses of Progression-Free Survival and Duration of Response

These censoring rules will be applied to PFS and DoR, as per Section 5.4.

Situation	Date of Progression or Censoring	Censoring Rule
Incomplete or no baseline tumor assessments	Cycle 1 Day 1 (in lieu of randomization)	Censored
Progression documented between scheduled visits	Earliest of: - Date progression assessment showing new lesion (if progression is based on new lesion) - Date of last progression assessment	Progressed
No progression	Date of last progression assessment with no documented progression	Censored
Treatment discontinuation for undocumented progression	Date of last progression assessment with no documented progression	Censored
Treatment discontinuation for toxicity or other reason	Date of last progression assessment with no documented progression	Censored
Next anti-lymphoma treatment started	Date of last progression assessment with documented non-progression before start of new treatment	Censored
Death before first PD assessment	Date of death	Progressed
Death between adequate assessment visits	Date of death	Progressed
Death or progression after more than one missed visit	Date of last progression assessment with documented non-progression	Censored

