7.4 Dose Modification Guidance and Safety Stopping Criteria

7.4.1 Dose Escalation Part (GEN3009 Monotherapy)

If a subject experiences a DLT, the subject may continue treatment with GEN3009, if the toxicity recovers to \leq Grade 2 or baseline within 4 weeks from occurrence of the DLT. Continued administration of GEN3009 must be agreed to between the sponsor and the investigator based on a thorough assessment of the event, the duration of the event, and benefit-risk for the subject. In the event a subject experiences a second episode of a DLT with GEN3009, the treatment will be permanently discontinued. Treatment with GEN3009 will be discontinued in the event the DLT is not resolved within 4 weeks.

- If a subject experiences toxicity that qualifies as a DLT but occurs after the 4-week DLT evaluation period, the subject's benefit-risk must be thoroughly assessed. Continued treatment with GEN3009 must be agreed between the sponsor and the investigator.
- For the subject who receives more than 4 doses of GEN3009, ie, treatment beyond the DLT evaluation period, all corresponding AEs that meet the DLT criteria will be considered for the purpose of determining the MTD and/or the RP2D. For the declaration of the RP2D of GEN3009 in the Expansion and for further development, the totality of the data from Dose Escalation (including safety, PK, pharmacodynamics, and preliminary efficacy will be evaluated).
- During the trial, a planned dose of GEN3009 can be postponed for up to 4 weeks from the last dose of trial drug for an AE whether it is considered drug-related or not.
- In case of dose delay of more than 4 weeks from the last trial drug administration due to toxicity, GEN3009 should be discontinued, unless approved by the sponsor's medical monitor.
- During the trial, the GEN3009 dose can be held for the following laboratory results:
 - a. If platelet count $<50 \times 10^9/L$, hold dose until platelet count is $\geq 50 \times 10^9/L$.
 - b. If febrile neutropenia $<0.5 \times 10^9/L$, hold dose until neutrophil count is $\geq 0.5 \times 10^9/L$.
 - c. If hemoglobin is <8 g/dL (<5 mmol/L), hold dose until hemoglobin ≥ 8 g/mL (>5 mmol/L).

Note: If the investigator deems any of the above cytopenia as bone marrow involvement due to the disease, continuation of GEN3009 treatment can be discussed with the sponsor's medical monitor. Transfusion with blood products and/or administration with G-CSF is permitted if needed (refer to Section [6.6.1](#)).

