11.1.2 Dose-Determining Analysis Set

In GEN3009 Dose Escalation, the dose-determining set (DDS) consists of all subjects from the safety set who have either received between 80% and 125% of the planned dose and have completed the DLT observation period, or have experienced a DLT during Cycle 1. A treated subject who discontinues due to toxicity during the DLT observation period should be included in the DDS, regardless of the amount of dose received. This constitutes an evaluable subject for the determination of MTD statistical analyses. Subjects enrolled in parallel cohorts during escalation will not be included in DDS, but will be reported in the FAS for decision making.

In GEN3009 + GEN3013 safety run-in, the DDS includes all FAS subjects in the safety run-in part who meet the minimum exposure criterion and have sufficient safety evaluations or experience a DLT during the DLT observation period. The DLT observation period consists of the 4 weeks, ie, 28 days, following the first GEN3009 dose.

A subject will meet the minimum exposure criterion if the subject takes at least 3 out of 4 pre-planned GEN3009 doses and one full dose of GEN3013 within the first cycle .

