The DDS consists of all subjects from the safety set who have either

- Received 80% - 125% of the planned dose
- Completed the DLT observation period
- Experienced a DLT during Cycle 1.

A treated patient who discontinues due to toxicity during the DLT observation period should be included in the DDS, regardless of the amount of dose received.

The DDS will be used for determination of the MTD, and will only be utilized during the Dose Escalation part. All subjects will be classified according to the dose level and treatment schedule (if applicable) which they received. Subjects who were treated with more than one dose level and treatment schedule by mistake will be classified according to the dose level and treatment schedule they received the longest, or the highest dose level (in the case of equal durations).

Response Evaluable Set (EFF)

The Response Evaluable set includes all subjects in FAS who have baseline evaluable disease and at least 1 post-baseline disease evaluation. Following the intent-to-treat principle, all subjects will be classified according to the dose level and treatment schedule to which they were assigned.

The Response Evaluable set will be used for sensitivity analyses during the primary and final analyses in the Dose Expansion part of the trial.

If not otherwise stated in the respective section, the statistical analyses will be performed for the following analysis sets:

Analyses	FAS	SAF	DDS	PAS	EFF
Demographics and baseline characteristics	✓	✓	✓		✓
Exposure and compliance	✓	✓	✓		
Previous and concomitant therapies	✓	✓			
Efficacy: Primary	✓				✓
Efficacy: Secondary	✓				✓
Safety		✓	✓		
Pharmacokinetics					✓

Should the FAS and SAF coincide, the analysis will be based on the FAS only and noted in table footnote. A similar approach applies to the FAS and EFF.

The data recorded in the screening log will be listed for the Screen Failures Analysis Set, if applicable.

5 General Statistical Methods and Definitions

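### SAP 14.1 ties all escalation-decision analyses to the Dose-Determining Set and names no FAS or Safety Set output for the parallel-cohort subjects whom protocol 11.1.2 wants decision-makers to see

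*SAP*

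**What the plan says.** SAP 14.1 describes what the Dose Escalation Committee (DEC) receives after each cohort. It fixes the population: "The Dose-Determining Set is used for all analyses to support dose escalation decisions". It then introduces its outputs with "The following statistical summaries and listings may be presented" and names three: demographics, "Summary of TEAEs during the DLT observation period", and an AE listing by dose level and subject. It adds a second route: "Dose escalation decisions may also be made based on raw data listings from the clinical database".

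Protocol 11.1.2 says: "Subjects enrolled in parallel cohorts during escalation will not be included in DDS, but will be reported in the FAS for decision making". Its DDS requires 80–125% of the planned dose together with completion of the DLT period, or else a DLT in Cycle 1. Discontinuation for toxicity within the DLT period also qualifies.

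SAP Section 4 defines the DDS differently. It begins "The DDS consists of all subjects from the safety set who have either" and prints three separate bullets: the 80–125% dose range, "Completed the DLT observation period", and a DLT in Cycle 1. It has the same rule for toxicity discontinuation but no exclusion of parallel cohorts.

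Protocol 7.4.1 adds that for subjects treated beyond the DLT period "all corresponding AEs that meet the DLT criteria will be considered for the purpose of determining the MTD and/or the RP2D".

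**The concern.** The DDS is the right denominator for the DLT rate. It is the wrong population for a general safety review, because its purpose is to exclude people. Protocol 4.1.1 bases committee recommendations on all the data available, and 4.1.1.1 refers to cumulative safety data. If the TEAE table and AE listing are confined to the DDS, the planned outputs cannot show AEs in parallel-cohort subjects, although the protocol wants those subjects reported to the people making the decision. This is a first-in-human escalation, and these are the only outputs the SAP lists for its dose steps.

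**Working it through.** **The plan's own figures.** With target φ = 0.25, φ1 = 0.6φ = 0.15 and φ2 = 1.4φ = 0.35:

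- λ1 = ln[(1−φ1)/(1−φ)] / ln[φ(1−φ1)/(φ1(1−φ))] = 0.1968
- λ2 = ln[(1−φ)/(1−φ2)] / ln[φ2(1−φ)/(φ(1−φ2))] = 0.2984

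Both match the stated 0.197 and 0.298. The row sums of protocol Table 34 (32.7, 32.1, 31.3, 32.3) match its totals (32.7, 32.0, 31.3, 32.2) within rounding. Nothing below alters the rule or the boundaries.

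**Who is in the DDS under each definition:**

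| Treated subject | Protocol 11.1.2 | SAP Section 4, bullets read as alternatives |
|---|---|---|
| mBOIN cohort, DLT in Cycle 1 | in | in |
| mBOIN cohort, stopped for toxicity in the DLT period | in | in |
| mBOIN cohort, DLT-free, completed 28 days, under 80% of dose | out | in |
| mBOIN cohort, DLT-free, left early for another reason | out | in only if 80–125% of dose was received |
| Parallel cohort, completed 28 days | out | in |

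**Consequence under the protocol's DDS.** The last three rows are missing from the 14.1 TEAE summary and AE listing. For parallel cohorts this conflicts directly with 11.1.2. For the others it only fits poorly with 4.1.1 and 4.1.1.1, because 11.1.2 promises FAS reporting for parallel cohorts alone. The loss can occur within one cohort: 4.1.1.1 allows the rule to run on two evaluable subjects when the third is not evaluable, provided neither of the two had a related AE of Grade 2 or higher. The third subject, one of three, would then be absent from the tables unless that subject had a DLT or stopped for toxicity.

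**Consequence under the SAP's DDS.** The subjects reappear in the tables but also enter the set used for the DLT rate. That is contrary to 11.1.2. For parallel cohorts it also conflicts with 4.1.1.1, where their DLTs do not directly feed the evaluation of the higher level. Membership can matter: 1 DLT in 5 is 0.200, between the boundaries, so stay; 1 in 6 is 0.167, below λ1, so escalate. Table 22 agrees in both cases. This illustrates sensitivity and does not predict an error.

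**Size of the parallel group, cumulative maximum:**

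- Protocol 4.1.1.1 and 11.11: 49/90 = 54%
- SAP 3.6: 28/60 = 47%
- Against Table 34's expected mBOIN sizes: 49/(49+32.7) = 60% to 49/(49+31.3) = 61%

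**Time window.** The TEAE summary stops at the DLT period. The AE listing has no such limit. AEs after Day 28 that meet the DLT criteria, which 7.4.1 brings into the MTD/RP2D decision, have no summary in 14.1.

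**The case against.** The strongest reply is that the committees are not confined to these tables. The tables are optional, raw listings are permitted and tied to no analysis set, and the DEC also reviews the safety data. Parallel-cohort DLTs go to the DMC (protocol 4.1.1.1), and the sponsor's safety committee monitors all treatment-emergent data (10.9). SAP 1.2 plans safety analyses on all subjects at the end of escalation, and 7.4.1 concerns the MTD/RP2D rather than each step. The DMC charter is not available here. All of this stands, and it rules out reading 14.1 as hiding data from decision-makers. It does not supply the FAS report that 11.1.2 calls for: raw listings are optional and have no stated population.

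A second reply is that the SAP was written to protocol v4.0, whereas the protocol supplied is v7.0, whose change log records a revised statistics section. Whether v4.0 contained the FAS sentence cannot be established. The mismatch is therefore shown only against the current protocol.

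A reader might also infer that the tables selectively lose subjects whose dosing was cut by toxicity, so that dose levels look cleaner than they are. Missing one weekly dose of four gives 3/4 = 75%, below 80%, and neutropenia occurred in 94.4% of the first 18 subjects. The documents do not support the inference. Both definitions retain anyone with a Cycle 1 DLT or a toxicity discontinuation. Protocol 2.1.4.1 says counts typically recovered by the next dose, and all 18 treated subjects were evaluated for DLTs (1+1+1+4+4+4+3 = 18). Parallel subjects go to levels already considered safe, so leaving them out has no demonstrated direction.

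**Conclusion.** The point holds as a conflict between the SAP and the current protocol over which treated subjects the escalation safety outputs cover. It does not depend on which DDS definition is applied: the protocol's leaves subjects out of the TEAE summary and AE listing, and the SAP's lets them into the DLT-rate set. It is more than missing detail, because it changes who appears in the committee's tables, and SAP 14.2 already uses the FAS or Safety Set, early withdrawals included, for the Expansion safety interim.

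The shares of 54% and 47% assume that every parallel slot and the full planned escalation sample are used. They are reached only cumulatively, and no figure is available for an individual decision. They should not be read as the fraction missing at each step. The conclusion is that tables may be incomplete; neither withheld data nor bias is shown. The conflict with 11.1.2 on omission from the tables covers parallel cohorts only.

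**What to change.** 1. Reword SAP 14.1 so that the DDS governs the DLT rate and the mBOIN recommendation only.
2. Base the TEAE summary and AE listing for dose decisions on the FAS/Safety Set (protocol 11.1.1 gives the two the same definition), at all dose levels, with parallel-cohort and non-evaluable subjects flagged.
3. Add a cumulative TEAE column beside the DLT-period column, so that later AEs meeting the DLT criteria are visible for the MTD/RP2D decision.
4. Align the SAP Section 4 DDS definition with protocol 11.1.2: dose range and completion jointly required, or a DLT; parallel cohorts excluded; the toxicity-discontinuation rule kept.

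The cost is minor SAP edits and one extra block in an existing table. The mBOIN rule, its boundaries and the sample size are unchanged.

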Appendix II: Categorization of Countries

Main Region	Region	Country
Northern America	Northern America	United States
Europe	Northern Europe	Denmark
	Southern Europe	Spain
	Western Europe	Netherlands

The following appendices will be produced following the finalization of the SAP.

Appendix III: Proposed List of Tables

Appendix IV: Proposed List of Listings

Appendix V: Proposed List of Figures
